At the Randomization Visit (Visit 2) eligible subjects will complete the Visit 2 assessments and take the first dose of study drug at the clinic and enter a 6-week Titration Period. The recommended LCM (or matching placebo) dosing during the Titration Period to achieve the target Maintenance Period doses is provided in [Table 7-1](#). All subjects should follow the recommended dosing schedule, unless dose adjustments based on tolerability are needed. [Table 7-2](#) provides LCM (or matching placebo) dosing with flexibility based on tolerability during the Titration Period. During the Titration Period, subjects must achieve a target Maintenance Period dose range (see [Table 7-3](#)).

During the Maintenance Period, a single dose reduction of study drug or placebo is permitted as long as the minimum target dose is maintained ([Table 7-3](#)). No other dose reductions are allowed. If a dose reduction is required, an (un)scheduled visit, either telephone or clinic visit, is required. If the subject is not able to tolerate the study drug after 1 dose reduction, the subject must enter the Taper Period and be withdrawn from the study. All dose reductions should be discussed with the Medical Monitor. Once the dose has been reduced, it cannot be increased.

The Treatment Period continues until 1 of the following occurs (whichever occurs first):

- Completion of ≥ 6 weeks of the Treatment Period and occurrence of ≥ 2 PGTC seizures
- Completion of 24 weeks of the Treatment Period without occurrence of 2 PGTC seizures
- The 125th event occurs in the study. A second PGTC seizure is defined as an event.

Subjects who experience > 2 PGTC seizures and who also complete ≥ 6 weeks (ie, ≥ 42 days) of the treatment period after randomization will be required to exit and complete the ET Visit ([Section 6.3](#)). The seizures may occur on the same day, but the initiation and completion of each individual seizure must be distinguishable allowing reliable counting of individual seizures.

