5.1.2 Study completers

The following subjects will be considered study completers:

- Subjects who meet any of the predetermined exit criteria (Section 6.3)
- Subjects who experience <2 PGTC seizures within the 24-week Treatment Period

Further information is provided in Section 6.3.

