^a The Treatment Period starts at the time of the Randomization Visit (Visit 2). The Treatment Period continues until 1 of the following occurs (whichever occurs first): completion of ≥6 weeks of the Treatment Period and occurrence of ≥2 PGTC seizures, or completion of 24 weeks of the Treatment Period without occurrence of 2 PGTC seizures.

^b Unscheduled Visits may be performed at any time after Visit 1 as clinic visits or TCs, at the discretion of the investigator. In addition to the required assessments indicated above, depending on the type of visit (clinic or telephone), further assessments can be completed as needed and may include ECG, vital signs, laboratory tests, etc. The C-SSRS must be performed (for subjects ≥6 years of age) if the unscheduled visit is due to an AE.

^c A window of ±2 days relative to Visit 1 is applicable for all protocol specified visits and TCs. During the Treatment Period, each visit should occur at the end of the week indicated in accordance with this time window.

^d All assessments at Visit 2 should be conducted prior to the first dose of study drug. At the end of the Prospective Baseline, subjects will be randomized at Visit 2 to receive LCM or placebo in a 1:1 fashion (active:placebo) and commence the Treatment Period with a 6-week, double-blind, flexible dose titration (see Section 7.2.1).

- ^e Subjects and/or caregivers will receive TCs throughout titration (Study Weeks 1, 3, and 5) to discuss titration dosing options.
- ^f Once the subject has experienced 2 PGTC seizures, the site may contact the Medical Monitor to confirm whether the subject has met the exit criteria. If the exit criteria are met, sites will be advised to have subjects return for their ET Visit within 1 week of the subject's second seizure (Section 6.3).
- ^g The complete physical examination will include cardiac and respiratory function via auscultation, and review of all body systems.
- ^h The brief physical examination will include review of the following body systems: cardiovascular, pulmonary, abdominal (hepato-gastrointestinal), and dermatologic.
- ⁱ The complete neurological examination will include selected assessments of mental status, sensory systems, motor functions, cranial nerves, reflexes, and coordination/cerebellar function.
- ^j The brief neurological examination will include selected assessments of general neurological status, reflexes, muscle strength, and coordination/cerebellar function.

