6.3 Exit criteria

Subjects will be required to exit the study if either of the following events occurs:

- Subject completes the first 6 weeks of the Treatment Period (after randomization) and experiences ≥ 2 PGTC seizures during that time
- Subject experiences a second PGTC seizure after the first 6 weeks of the Treatment Period
- The 125th event occurs in the study

Once the subject has experienced 2 PGTC seizures, the site should contact the Medical Monitor to confirm whether the subject has met the exit criteria. If the exit criteria are met, sites will be advised to have subjects return for their ET Visit within **1 week** of the subject's second seizure, with the following exception: if the 2 PGTC seizures occur during the first 6 weeks of the Treatment Period (after randomization), the subject should continue the Titration Period visits and wait for the end of the first 6 weeks of the Treatment Period to complete the ET Visit.

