9.3.1.1 PGTC seizures

The following information will be recorded on a daily basis as applicable:

- Seizure type
- Number of PGTC seizures

If more than 1 PGTC seizure occurs on a single day, each seizure should be counted separately, provided there is a complete recovery of consciousness between seizures.

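### Protocol 5.1 sets mandatory exit at more than two PGTC seizures, contradicting its own bullet and 6.3, and its same-day counting sentence is looser than 9.3.1.1

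*Protocol*

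**What the plan says.** **Exit threshold.** Section 5.1 first lists what ends the Treatment Period. One of its bullets is six completed weeks with two or more PGTC seizures. The next paragraph makes exit and the ET Visit mandatory, but begins "Subjects who experience > 2 PGTC seizures and who also complete" and refers to 6.3. Section 6.3 requires exit for two or more seizures within the first six weeks, or if "Subject experiences a second PGTC seizure after the first 6 weeks of the Treatment Period". Footnote a of Table 5-1 says the same as the 5.1 bullet: "completion of ≥6 weeks of the Treatment Period and occurrence of ≥2 PGTC seizures".

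**Same-day seizures.** Section 5.1 allows seizures on one day to count individually, on the condition that "the initiation and completion of each individual seizure must be distinguishable allowing reliable counting of individual seizures". Section 9.3.1.1, which describes how PGTC seizures are recorded, says that "each seizure should be counted separately, provided there is a complete recovery of consciousness between seizures".

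**Check at two seizures.** In 6.3, once a subject has had two seizures, "the site should contact the Medical Monitor to confirm whether the subject has met the exit criteria". Section 8.2.3.6 uses the same verb. Footnote f of Table 5-1 softens it: "the site may contact the Medical Monitor to confirm whether the subject has met the exit criteria".

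**The concern.** The trial counts second PGTC seizures, and the same count decides when a subject leaves blinded treatment. The text that sites work from should therefore give one threshold and one way of counting. Section 5.1 departs from the rest of the protocol on both.

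On the threshold, the sentence saying who must leave gives a different number from the criteria it cites. Section 5.4.2 justifies the design partly by letting subjects leave after two seizures instead of having more, so this number should be right everywhere.

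On counting, whether a same-day cluster is one seizure or two can decide whether, and on what date, a primary event is recorded. It also bears on the PGTC seizure-frequency variables in 4.1.3. Efficacy is taken from diary counts (9.3.1), so the rule matters when the diary is filled in and reviewed. A later analysis document cannot easily repair a count made under the wrong rule. The protocol plans 150 to 180 sites, and 5.1 does not point them to 9.3.1.1.

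**Working it through.** **The plan's own figure, for context.** Section 13.8 gives 125 events for 90% power at a hazard ratio of 0.56, two-sided 5%; allocation is 1:1 (5.1).
- Schoenfeld events = 4 × (1.960 + 1.282)² / (ln 0.56)² = 4 × 10.507 / 0.3362 = 125.02, or 126 rounded up. Power at 125 events is 0.89996.
- Hazard ratio: ln 0.482 / ln 0.254 = 0.533, and 0.533 × 1.05 = 0.560.

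The figures reproduce. None takes the exit threshold or the same-day rule as an input, so they are the same before and after correction. The rest is a comparison of text.

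**Threshold.** In the current text (amendment logs set aside):
- More than two: the 5.1 exit sentence only.
- Two, or the second seizure: the 5.1 bullets; the later 5.1 paragraph on entering EP0012; Table 5-1 footnotes a and f; 5.4.2; 6.3; 7.2.3; 8.2; 8.2.3.6; 8.3.1.2.

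Section 5.1.2 shows which is meant. Completers are subjects who meet an exit criterion, plus "Subjects who experience <2 PGTC seizures within the 24-week Treatment Period". With a threshold of three, a subject who reached Week 24 with exactly two seizures would fall in neither group (unless the 125th event had ended the study). With a threshold of two, the groups fit together.

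A misread symbol is unlikely. The greater-or-equal sign is read correctly twice in the same sentence, and the Amendment 2 log (17.4) carries the sentence with the same sign. The log is used here only to rule out a reading error.

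**Same-day count.** Take two seizures on one day:
- Starts and ends distinct, consciousness fully regained between them: two under 5.1, two under 9.3.1.1.
- Starts and ends distinct, consciousness not fully regained: two under 5.1, one under 9.3.1.1.
- Starts and ends not distinct: not countable as two under either.

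The rules are nested: whatever passes 9.3.1.1 passes 5.1, but not the reverse. Only the middle case differs. Appendix 17.8 describes attacks without recovery between them as status epilepticus, which fits 9.3.1.1. Section 6.4 lists status epilepticus requiring intervention as a possible reason for withdrawal, and 13.3.1 censors premature discontinuations at last dose. The middle case could therefore be a primary event under 5.1, or a single seizure under 9.3.1.1, followed by censoring if the subject is then withdrawn.

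**What is not touched.** The event is defined as the second seizure in 5.1 and 5.1.3, whatever the exit sentence says. The key secondary rests on time to first seizure, which neither discrepancy changes. The documents give no frequency for same-day clusters without recovery, so the number of events affected cannot be calculated.

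**The case against.** The case on the other side is that this is a one-character slip, already answered on the same page. The bullet above ends treatment at two. The sentence refers the reader to 6.3, which is correct and governs. In logic the sentence gives a sufficient condition: requiring exit above two does not forbid exit at two. On same-day seizures, 5.1 is a design overview stating a necessary condition, and 9.3.1.1 supplies the operational rule for the diary from which efficacy is derived. An overview completed by a later section is normal protocol structure. The verb in footnote f is a table-note variation, and that footnote also cites 6.3.

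Most of this stands. It defeats some stronger readings that a reader might infer:
- *Subjects with exactly two seizures are kept on treatment.* They are not. The 5.1 bullet and 6.3 already end treatment at two, and that result appears only if one sentence is cut off from both.
- *The primary event becomes the third seizure.* It does not; the event definition is separate and consistent.
- *Power, event numbers or the comparison between arms are damaged.* Nothing in the protocol shows this.
- *The softer verb in footnote f removes the Medical Monitor check.* Sections 6.3 and 8.2.3.6 still call for it, so the footnote has no independent effect.

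Two things survive. The sentence still states a threshold that contradicts the criteria it cites, in text that sites use. And 5.1 gives a condition for counting seizures without saying that a stricter rule applies elsewhere, so misuse by a site that reads only 5.1 is possible.

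**Conclusion.** The point holds as an internal inconsistency of minor severity. It is not a design choice: 5.1.2, 6.3 and the 5.1 bullet leave no doubt that two is meant. The wrong threshold has no consequence of its own where 6.3 is followed. The same-day sentence matters slightly more, because it can decide whether a primary event is reported, but only for a cluster with distinct seizures and incomplete recovery at a site that relies on 5.1 alone. The conclusion takes 6.3 as governing exit and 9.3.1.1 as governing the diary count, which is the natural reading of the protocol. No size in events can be given, and no effect on power or bias is claimed.

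**What to change.** 1. In the 5.1 exit sentence, change > 2 to ≥ 2.
2. Replace the 5.1 same-day sentence with a reference to 9.3.1.1 as the single rule for counting PGTC seizures, and use that rule in the diary instructions.
3. Optional tidying: in Table 5-1 footnote f, change may to should, to match 6.3 and 8.2.3.6.

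The cost is two wording corrections, a third if the footnote is aligned, and a short memo to sites. No extra data, analysis or change to the sample size is needed.

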5.1.1 Study duration per subject

The maximum duration of study drug administration is 28 weeks. The study will last a maximum of 36 weeks per subject, consisting of the following study periods:

- 4-week Prospective Baseline Period
- 6-week (minimum) to 24-week (maximum) Treatment Period (including a 6-week titration)
- 4-week End of Study Period consisting of either:
 - 4-week blinded transition (required for subjects participating in EP0012)
 - Up to 4-week blinded taper followed by a 30-day Safety Follow-up Period (required for subjects not participating in EP0012)
 - Subjects can enter EP0012 after the completion of Visit 10 (Week 24) or ET Visit and a 4-week blinded transition. Subjects who choose not to continue in EP0012 must complete an up to 4-week blinded taper followed by a 30-day Safety Follow-up Period (see Section 7.2.4).

Titration Period

In case the 125th event occurs in the study while subjects are still in their 6-week Titration Period, these subjects will not have to proceed to Week 6 prior to initiating the Transition/Taper Period; these subjects will also be invited for their ET Visit at the next scheduled visit.

Maintenance Period

In case the 125th event occurs in the study while subjects are in their Maintenance Period, these subjects will also be invited for their ET Visit at the next scheduled visit and enter the Transition/Taper Period.

Transition Period

In case the subject is in the Transition/Taper Period, these subjects will proceed to their scheduled completion visit.

Screening Period

In case the 125th event occurs while a subject is in screening, the subject may proceed to the scheduled Baseline Visit if they are eligible or are a Baseline failure; these subjects will be able to enter EP0012 and will not proceed to randomization in SP0982 but will enter EP0012. For the subjects entering EP0012, their next visit will be Visit 1.

The end of the study is defined as the date of the last visit of the last subject in the study.

5.1.2 Study completers

The following subjects will be considered study completers:

- Subjects who meet any of the predetermined exit criteria (Section 6.3)
- Subjects who experience <2 PGTC seizures within the 24-week Treatment Period

Further information is provided in Section 6.3.

5.1.3 Planned number of subjects and sites

The number of screened subjects may vary according to the observed screen failure rate. Up to 250 subjects (100 to 125 per treatment arm) will be randomized to achieve a total of 125 events, where an event is defined as the occurrence of the second PGTC seizure.

Subjects will be randomized in the following age categories:

- (a) ≥ 4 years of age to <12 years of age
- (b) ≥ 12 years of age to <18 years of age
- (c) ≥ 18 years of age category

There will be approximately 150 to 180 sites in order to recruit the required subjects; additional sites will be added if deemed necessary. A target of at least 40 of the randomized subjects should consist of subjects <18 years of age.

5.1.4 Anticipated regions and countries

The study is planned to be conducted in the US, Europe, Asia, and Australia, with possible extension to other countries and regions.

5.2 Schedule of study assessments

The schedule of study assessments is provided in Table 5–1, Table 5–2, and Table 5–3.

Table 5–1: Schedule of study assessments for SP0982 (Prospective Baseline, Titration Period, Titration Period, Maintenance Period, ET Visit, and Unscheduled Visits)

| Assessments | Prospective Baseline 4 weeks | | Treatment Period ^a | | | | | | | | | | Unscheduled ^b | | |
|---|------------------------------|----|---|----|----|----|----|----|-------------------------------|----|----|----|--------------------------|-------|----|
| | V1 ^{bb} | TC | Titration Period (6 weeks) ^c | | | | | | Maintenance Period (18 weeks) | | | | | | NA |
| | | | TC | V3 | TC | V4 | TC | V5 | V6 | V7 | V8 | V9 | V10/ET ^t | | |
| Study week | -4 | -2 | 1 | 2 | 3 | 4 | 5 | 6 | 8 | 12 | 16 | 20 | 24 | Visit | NA |
| Informed consent/assent | X | | | | | | | | | | | | | | |
| Inclusion/Exclusion criteria | X | X | | | | | | | | | | | | | |
| Subject ID card dispensing | X | | | | | | | | | | | | | | |
| Concomitant medications and AED(s) | X | X | X | X | X | X | X | X | X | X | X | X | X | X | X |
| Medical history/Epilepsy history | X | | | | | | | | | | | | | | |
| Physical exam (complete) ^g | X | X | | | | | | | | | | | | | X |
| Physical exam (brief) ^h | | | | X | | | | X | X | X | X | X | X | | |
| Neurological exam (complete) ^l | X | | | | | | | | | | | | | | |
| Neurological exam (brief) ^l | | | | X | | | | X | X | X | X | X | X | | |
| 12-lead ECG ^k | X | | | X | | | | X | X | X | X | X | X | | |
| Vital signs (BP and pulse) including orthostatic assessments ^l | X | X | X | X | X | X | X | X | X | X | X | X | X | X | X |
| Body weight | X | | | | | | | X | X | X | X | X | X | | |
| Height | X | | | | | | | | | | | | | | |
| EEG ^m | X | | | | | | | | | | | | | | |
| Tanner Stage ⁿ | | | | | | | | | | | | | | | X |
| Laboratory tests: | | | | | | | | | | | | | | | |
| Chemistry/hematology | X | | | X | | | | | X | | | | | X | |
| Endocrinology ^{aa} | X | | | | | | | | | | | | | | X |
| Urinalysis ^o | X | | | X | | | | | X | | | | | X | |
| Pregnancy test ^p | X | | | X | | | | | X | | | | | X | |
| LCM plasma concentration ^q | | | | | | | | | | | | | | | |
| Contact IRT ^r | X | | | X | | | | | X | | | | | X | X |
| Randomization | | | | | | | | | | | | | | | |
| Dispense subject diary ^s | | | | X | | | | | X | | | | | X | X |
| Subject diary return/review ^s | | | | X | | | | | X | | | | | X | X |
| Dispense study drug ^t | | | | X | | | | | X | | | | | X | X |
| Study drug review/return | | | | X | | | | | X | | | | | X | X |
| Withdrawal criteria | X | X | X | X | X | X | X | X | X | X | X | X | X | X | X |

Table 5–1: Schedule of study assessments for SP0982 (Prospective Baseline, Titration Period, Maintenance Period, ET Visit, and Unscheduled Visits)

| Assessments | Prospective Baseline 4 weeks | | Treatment Period ^a | | | | | | Unscheduled ^b | | | | | | |
|---|------------------------------|----|---|----|-------------------------------|----|----|----|--------------------------|----|----|----|----|----|---------------------|
| | 6 to 24 weeks (maximum) | | Titration Period (6 weeks) ^c | | Maintenance Period (18 weeks) | | | | | | | | | | |
| | V1 ^{bb} | TC | V2 ^d | TC | V3 | TC | V4 | TC | | V5 | V6 | V7 | V8 | V9 | V10/ET ^f |
| Study week | -4 | -2 | | 1 | 2 | 3 | 4 | 5 | 6 | 8 | 12 | 16 | 20 | 24 | NA |
| AE reporting | X | X | X | X | X | X | X | X | X | X | X | X | X | X | X |
| Achenbach CBCL ^y | | | X | | | | | | | | | | | | X |
| BRIEF-P/BRIEF ^w | | | X | | | | | | | | | | | | X |
| EQ-5D-3L ^x | | | X | | | | | | | | | | | | X |
| QOLIE-31-P/PedsQL ^y | | | X | | | | | | | | | | | | X |
| C-SSRS ^z | X | | X | X | X | X | X | X | X | X | X | X | X | X | X |
| Healthcare resource use | | | X | X | X | X | X | X | X | X | X | X | X | X | X |
| Work/school days lost due to epilepsy | | | X | X | X | X | X | X | X | X | X | X | X | X | X |
| Days with help from a caregiver due to epilepsy | | | X | X | X | X | X | X | X | X | X | X | X | X | X |
| Socio-professional data | | | X | X | X | X | X | X | X | X | X | X | X | X | X |

AE=adverse event; AED=antiepileptic drug; bid=twice daily; BP=blood pressure; exam=examination; BRIEF=Behavior Rating Inventory of Executive Function; BRIEF-P=Behavior Rating Inventory of Executive Function-Preschool Version; CBCL=Child Behavior Checklist; C-SSRS=Columbia-Suicide Severity Rating Scale; ECG=electrocardiogram; EEG=electroencephalogram; EQ-5D-3L=EuroQol-5D; ET=Early Termination; ID=identification; IEC=Independent Ethics Committee; IGE=idiopathic generalized epilepsy; IRB=Institutional Review Board; IRT=interactive response technology; LCM=lacosamide; NA=not applicable; PEDsQL=Pediatric Quality of Life Inventory; PGTC=primary generalized tonic-clonic; QOLIE-31-P=Patient-Weighted Quality of Life in Epilepsy Inventory-Form 31; TC=telephone contact; V=Visit

^a The Treatment Period starts at the time of the Randomization Visit (Visit 2). The Treatment Period continues until 1 of the following occurs (whichever occurs first): completion of ≥6 weeks of the Treatment Period and occurrence of ≥2 PGTC seizures, or completion of 24 weeks of the Treatment Period without occurrence of 2 PGTC seizures.

^b Unscheduled Visits may be performed at any time after Visit 1 as clinic visits or TCs, at the discretion of the investigator. In addition to the required assessments indicated above, depending on the type of visit (clinic or telephone), further assessments can be completed as needed and may include ECG, vital signs, laboratory tests, etc. The C-SSRS must be performed (for subjects ≥6 years of age) if the unscheduled visit is due to an AE.

^c A window of ±2 days relative to Visit 1 is applicable for all protocol specified visits and TCs. During the Treatment Period, each visit should occur at the end of the week indicated in accordance with this time window.

^d All assessments at Visit 2 should be conducted prior to the first dose of study drug. At the end of the Prospective Baseline, subjects will be randomized at Visit 2 to receive LCM or placebo in a 1:1 fashion (active:placebo) and commence the Treatment Period with a 6-week, double-blind, flexible dose titration (see Section 7.2.1).

- ^e Subjects and/or caregivers will receive TCs throughout titration (Study Weeks 1, 3, and 5) to discuss titration dosing options.
- ^f Once the subject has experienced 2 PGTC seizures, the site may contact the Medical Monitor to confirm whether the subject has met the exit criteria. If the exit criteria are met, sites will be advised to have subjects return for their ET Visit within 1 week of the subject's second seizure (Section 6.3).
- ^g The complete physical examination will include cardiac and respiratory function via auscultation, and review of all body systems.
- ^h The brief physical examination will include review of the following body systems: cardiovascular, pulmonary, abdominal (hepato-gastrointestinal), and dermatologic.
- ⁱ The complete neurological examination will include selected assessments of mental status, sensory systems, motor functions, cranial nerves, reflexes, and coordination/cerebellar function.
- ^j The brief neurological examination will include selected assessments of general neurological status, reflexes, muscle strength, and coordination/cerebellar function.
- ^k The ECG recordings should be performed at the same time of day (when possible) and prior to blood sample collection and vital sign assessments. Care should be taken to assure proper lead placement and quality ECG recordings. If possible, subjects should rest in a supine position at least 5 minutes prior to each recording and should be motionless during the recording. In pediatric subjects (<18 years of age), 12-lead ECGs (2 interpretable recordings) approximately 20 to 30 minutes apart must be performed.
- ^l Blood pressure measurements should be taken with the proper placement and proper sized cuff to obtain accurate measurements.
- ^m Subjects are required to have had an EEG showing discharges consistent with IGE prior to Visit 1. A confirmatory EEG may be performed during the Prospective Baseline, if approved by the Central Reviewer. Investigators will send a copy of the EEG report to the Central Reviewer. The information provided will be reviewed and any questions regarding the subject's eligibility will be discussed with the investigator prior to the subject being randomized.
- ⁿ The Tanner Stage will be performed only for subjects who are pubescent at Visit 2 or who enter puberty during the course of the study.
- ^o Urinalysis will be required for all subjects.
- ^p Serum pregnancy tests will be conducted at the following visits: Visit 1, Visit 10/ET Visit. At Visit 2, a urine dipstick pregnancy test should be performed prior to IRT contact. The result of the urine dipstick test must be negative prior to administration of the first dose of study drug. All other pregnancy tests (ie, Visits 3 through Visit 9) will be urine dipstick. Pregnancy tests will be performed for female subjects of childbearing potential only.
- ^q Blood samples for analysis of LCM plasma concentrations will be collected at any time between 2 successive bid doses.
- ^r An IRT will be used to control all drug distribution and inventory for this study.
- ^s At all visits, subjects and/or caregivers will be reminded to report the occurrence of all seizure types, including days without seizures.
- ^t During the Maintenance Period, a single dose reduction is allowed as long as the minimum target dose is maintained (see Table 7-3). Once the dose has been reduced, it cannot be increased. Subjects who are not able to tolerate the minimum target dose during the Maintenance Period will be withdrawn from the study. All dose reductions should be discussed with the Medical Monitor.
- ^u At Visit 2, subjects should take the first dose of study drug in the clinic.
- ^v The Achenbach CBCL/1½-5 is for children <5 years and 11 months of age and the CBCL/6-18 is for children ≥6 years to <18 years of age; the questionnaire is to be completed by the parent(s)/legal representative(s) (estimated completion time 45 minutes). For each subject, the same version of the scale that was completed at Visit 2 (CBCL/1½-5 or CBCL/6-18) should be maintained for the duration of the study and should be completed by the same parent/legal representative.
- ^w The BRIEF-P should be used for subjects who are <5 years of age at Visit 2 and the BRIEF should be used for subjects who are ≥5 years of age at Visit 2. The same version of the scale that was completed at Visit 2 (BRIEF-P or BRIEF) should be maintained for each subject for the duration of the study.

- x The EQ-5D-3L will be performed in subjects who are ≥ 12 years of age.
- y The QOLIE-31-P will be performed for subjects who are ≥ 18 years of age and the PedsQL will be performed for subjects < 18 years of age. The version of the PedsQL used should be consistent with the subject's age at Visit 2 and should be maintained for each subject for the duration of the study.
- z The C-SSRS will be completed for all subjects ≥ 6 years of age.
- aa Thyroid function will be required in subjects < 18 years of age only.
- bb Participation in the study starts from the time of signing the approved Informed Consent/Assent form. However, sites may conduct prescreening EEGs and prior to this, subjects will read and sign a separate Informed Consent form that has been approved by an IRB/IEC, and the Sponsor, and which complies with regulatory requirements.

REDACTED COPY

For information purposes only. This document cannot be used to support any marketing authorization application and any extensions thereof.

Table 5–2: Schedule of study assessments for SP0982 (Transition Period)

| Assessment | Transition Period (4 weeks) ^a | |
|---|---|--|
| | Transition TC or Visit ^b | Final Clinic Visit (EP0012 Visit 1) |
| | 2 weeks after Visit 10/ET | |
| Concomitant medications and AED(s) | X | X |
| Body weight | | X |
| Height | | X |
| Physical exam (complete) ^d | | X |
| Neurological exam (complete) ^c | | X |
| 12-lead ECG ^f | | X |
| Vital signs (BP and pulse) including orthostatic assessments ^c | | X |
| Laboratory tests: | | |
| Chemistry/hematology | | X |
| Urinalysis ⁱ | | X |
| Endocrinology ^k | | X |
| Pregnancy test ^l | | X |
| Contact IRT | | X |
| Subject diary return/review ^g | | X |
| Study drug review/return | | X |
| Withdrawal criteria | X | X |
| AE reporting | X | X |
| C-SSRS ^h | | X |
| Healthcare resource use | | X |
| Work/school days lost due to epilepsy | | X |
| Days with help from a caregiver due to epilepsy | | X |
| Socio-professional data | | X |

AE=adverse event; AED=antiepileptic drug; BP=blood pressure; C-SSRS=Columbia-Suicide Severity Rating Scale; ECG=electrocardiogram; ET=Early Termination; IRT=interactive response technology; TC=telephone contact

Note: For all transition visits, a window of ±2 days relative to Visit 1 (Baseline Period) is applicable. Each visit should occur at the end of the week indicated in accordance with this time window.

^a At the end of Visit 10/ET, subjects who complete the study may be eligible to participate in an open-label extension study (EP0012). Subjects who choose to enroll in the open-label extension study will proceed to a blinded 4-week Transition Period.

^b A Transition TC is required. A Transition Clinic Visit is optional, at the discretion of the investigator. Subjects requiring a clinic visit will have the same assessments conducted as an Unscheduled Visit.

^c Blood pressure measurements should be taken with the proper placement and proper sized cuff to obtain accurate measurements.

^d The complete physical examination will include cardiac and respiratory function via auscultation, and review of all body systems.

-
- ^e The complete neurological examination will include selected assessments of mental status, sensory systems, motor functions, cranial nerves, reflexes, and coordination/cerebellar function.
 - ^f The ECG recordings should be performed at the same time of day (when possible) and prior to blood sample collection and vital sign assessments. Care should be taken to assure proper lead placement and quality ECG recordings. If possible, subjects should rest in a supine position at least 5 minutes prior to each recording and should be motionless during the recording. In pediatric subjects (<18 years of age), 12-lead ECGs (2 interpretable recordings) approximately 20 to 30 minutes apart must be performed.
 - ^g The subject diary will be dispensed at Visit 1. At all subsequent visits, subjects and or caregivers will be reminded to report the occurrence of all seizure types, including days without seizures.
 - ^h The C-SSRS will be completed for all subjects ≥ 6 years of age.
 - ⁱ Urinalysis will be required for all subjects.
 - ^j Urine pregnancy tests will be performed for female subjects of childbearing potential only.
 - ^k Thyroid function will be required in subjects <18 years of age only.

This document cannot be used to support any marketing authorization application and any extensions or variations thereof.

REDACTED COPY

Table 5–3: Schedule of study assessments for SP0982 (Taper Period and Safety Follow-up Period)

| Assessment | Taper Period ^a (up to 4 weeks) | Safety Follow-up Period ^c | |
|--|--|---|--|
| | End of Taper Visit ^b | Safety Follow-up Visit | Safety Follow-up TC |
| | | 2 weeks (±2 days) after last dose of study drug | 30 days (-1/+3 days) after last dose of study drug |
| Concomitant medications and AED(s) | X | X | X |
| Physical exam (complete) ^k | X | X | |
| Neurological exam (complete) ^l | X | X | |
| 12-lead ECG ^h | X | X ⁱ | |
| Vital signs (BP and pulse) including orthostatic assessments ^j | X | X | |
| Body weight | X | X | |
| Laboratory tests: | | | |
| Chemistry/hematology | X | X ⁱ | |
| Endocrinology ^m | | X ⁱ | |
| Urinalysis ^f | X | X | |
| Pregnancy test ^g | X | X | |
| Contact IRT | X | | |
| Subject diary return/review ^d | X | | |
| Study drug review/return | X | | |
| Withdrawal criteria | X | | |
| AE reporting | X | X | X |
| C-SSRS ^e | X | X | |
| Healthcare resource use | X | X | |
| Work/school days lost due to epilepsy | X | X | |
| Days with help from a caregiver due to epilepsy | X | X | |
| Socio-professional data | X | X | |

AE=adverse event; AED=antiepileptic drug; BP=blood pressure; C-SSRS=Columbia-Suicide Severity Rating Scale; ECG=electrocardiogram; ET=early termination; IRT=interactive response technology; TC=telephone contact

[figure not shown]
- ^a Subjects completing Visit 10 (Week 24) or the ET Visit who choose not to continue in EP0012 must complete a blinded taper followed by the End of Taper Visit.
- ^b An End of Taper Visit will be scheduled at the end of the Taper Period (up to 4 weeks) depending on dose level achieved; see Table 7-5. Of note, for subjects who enter the Taper Period at ≤ 2 mg/kg/day (oral solution) or 100mg/day (tablets), the End of Taper Visit will take the place of the ET Visit.
- ^c There will be a 30-day (-1/+3 days) Safety Follow-up Period for subjects who complete the End of Taper Visit. The Safety Follow-up Period consists of a clinic visit 2 weeks after the End of Taper Visit followed 2 weeks later by a TC. After the 125th event occurs, the 30-day Safety Follow up Period will be done as part of EP0012, except if the subject refuses to sign the EP0012 informed consent form. If the subject signs the informed consent form for a short Safety Follow-up as part of EP0012, the 30-day Safety Follow-up will be performed as part of EP0012; otherwise, the Safety Follow-up will be performed in SP0982.
- ^d The last subject diary will be returned at the End of Taper Visit.
- ^e The C-SSRS will be completed for all subjects ≥ 6 years of age.
- ^f Urinalysis will be required for all subjects.
- ^g Urine pregnancy tests will be performed for female subjects of childbearing potential only.
- ^h The ECG recordings should be performed at the same time of day (when possible) and prior to blood sample collection and vital sign assessments. Care should be taken to assure proper lead placement and quality ECG recordings. If possible, subjects should rest in a supine position at least 5 minutes prior to each recording and should be motionless during the recording. In pediatric subjects (<18 years of age), 12-lead ECGs (2 interpretable recordings) approximately 20 to 30 minutes apart must be performed.
- ⁱ The assessment will be required only for subjects with an abnormal value (clinical chemistry, hematology, or endocrinology) or reading (ECG) at the previous clinic visit.
- ^j Blood pressure measurements should be taken with the proper placement and proper sized cuff to obtain accurate measurements.
- ^k The complete physical examination will include cardiac and respiratory function via auscultation, and review of all body systems.
- ^l The complete neurological examination will include selected assessments of mental status, sensory systems, motor functions, cranial nerves, reflexes, and coordination/cerebellar function.
- ^m Thyroid function will be required in subjects <18 years of age only.

